11.1.3. Reporting Results

The least squares (LS) mean, standard error (SE) of the LS mean, two-sided 95% confidence interval (CI) of the LS mean and p-value will be reported at each time point. Statistical testing will be performed at every time point that eGFR is measured. The change from baseline in

eGFR at Week 12 is the primary endpoint. A formal test of mean change from baseline in eGFR $\neq 0$ will be conducted at Week 12. The mean change from baseline in eGFR at all other time points will be considered exploratory, so tests at these time points will be performed with no adjustments for multiple comparisons.

A plot of the LS means with 95% CIs of change from baseline in eGFR value over time will be presented.

Descriptive statistics for observed eGFR values and change from baseline in eGFR values will be provided by time point through the end of follow-up. A plot of mean and standard error of eGFR values over time will be presented.

11.2. Additional Efficacy Analyses

[REDACTED]

[REDACTED]	[REDACTED]
[REDACTED]	[REDACTED]
[REDACTED]	[REDACTED]
[REDACTED]	[REDACTED]
[REDACTED]	[REDACTED]
[REDACTED]	[REDACTED]
[REDACTED]	[REDACTED]
[REDACTED]	[REDACTED]

11.2.2. Historical eGFR Slope Dataset

Up to 5 years of historical serum creatinine values will be collected for each patient as part of their medical history information. Serum creatinine values will be converted to mg/dL and eGFR will be calculated according to the equations in 7.1.3 using the patient age at laboratory collection. Historical serum creatinine values will have been analyzed at various local laboratories (i.e., not collected as part of central lab data). Historical serum creatinine values will be converted to mg/dL if not entered in those units. Therefore, historical serum creatinine and eGFR values will be treated separately from data collected as part of the trial's central lab assessments.

One dataset will be generated with the baseline eGFR values, baseline log(ACR) values, the historical eGFR values, and the eGFR results in PHOENIX that were used in the primary efficacy analysis (Section 7.3 and Section 11.1). The analysis time points are defined as follows:

Table 5: Comparison of eGFR Slope in PHOENIX vs. Historical eGFR Slope

Analysis Time Point	Study Day Windows
Historical	1825 to 1 days prior to Screen A
Baseline	Screen A to Day 1
On Treatment	Day 2 to Day 98

The eGFR values used in the analysis datasets for the baseline label will be the baseline eGFR values for each patient (defined in 7.2.1), not the individual Screen A, Screen B, and Day 1

eGFR values. The continuous year will be calculated as a continuous variable as Study Day / 365.25. Historical values will have a negative Study Day value, calculated as Date of Lab Collection – Date of Day 1 Study Day. Week 16 values will not be included in the analysis. Baseline eGFR values will have a continuous year value of zero.

A separate dataset will be generated for summary statistics of historical and on-treatment results, for patients with historical eGFR data entered. The second date will separate the historical and on-treatment results by year to calculate summary statistics, but will not be used in the statistical model described in Section 11.2.3.

Table 6. Labels for Summary of Historical and On-Treatment Change in eGFR

Label	Study Day Windows
Historical Year 5	Day -1825 Before Screen A to Day -1461 Before Screen A
Historical Year 4	Day -1460 Before Screen A to Day -1096 Before Screen A
Historical Year 3	Day -1095 Before Screen A to Day -731 Before Screen A
Historical Year 2	Day -730 Before Screen A to Day -366 Before Screen A
Historical Year 1	Day -365 Before Screen A to Day -1 Before Screen A
Baseline	Day -60 to Day 1
Year 1	Day 2 to Day 98

The summary statistics will include the average GFR value by patient and analysis time point. For instance, if multiple values are listed in the year 1 results for a given patient, the average of those values will be used to calculate the summary statistics. However, all eGFR values will be used in the statistical model described in Section 11.2.3.

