## Diagnosis and main criteria for inclusion:

- Male and female patients 18 ≤ age ≤ 65 upon study consent;
- Screening eGFR (average of Screen A and Screen B eGFR values) ≥ 30 and ≤ 90 mL/min/1.73 m^2. The two eGFR values collected at Screen A and Screen B visits used to determine eligibility must have a percent difference ≤ 25%;
- Albumin to creatinine ratio (ACR) ≤ 2500 mg/g at Screen B visit;
- 4. If receiving an angiotensin-converting enzyme (ACE) inhibitor and/or an angiotensin II receptor blocker (ARB), patients should be prescribed the maximally tolerated labeled daily dose (MTLDD), as defined in Section 9.1.7, for at least 6 weeks prior to the Screen A visit. The dosage of ACE inhibitor and/or ARB should remain the same throughout the remainder of the study (i.e., no change in dosage or medication), and any potential changes should be discussed with the medical monitor. Patients not taking an ACE inhibitor and/or ARB because of a medical contraindication may be eligible if they have discontinued treatment at least 8 weeks prior to the Screen A visit (these patients must be discussed with the medical monitor prior to enrollment);
- For patients enrolling in T1D Cohort:
  - a. Diagnosis of type 1 diabetes confirmed by fasting C-peptide level. Diagnosis must have been made ≤ 35 years of age;
  - Prescribed stable dose of insulin to maintain adequate glucose control for at least 6 months prior to the Screen A visit;
- For patients enrolling in IgAN Cohort:
  - Biopsy-confirmed IgA nephropathy;
- For patients enrolling in FSGS Cohort:
  - Biopsy-confirmed FSGS that is not due to known secondary causes including morbid obesity, decreased renal mass, viral infections, drug-induced nephrotoxicity, or prior history of vasculitis;
- 8. For patients enrolling in ADPKD Cohort:
  - a. Genetic confirmation of PKD1 mutation;
- Adequate bone marrow reserve and organ function at the Screen A visit as follows:
  - a. Hematologic: Absolute neutrophil count > 1.5 x  $10^{\circ}/L$ , platelets >  $100 \times 10^{\circ}/L$ , hemoglobin (Hgb)  $\geq 9 \text{ g/dL}$ ;
  - Hepatic: Total bilirubin (TBL) ≤ 1.5X the upper limit of normal (ULN), alanine aminotransferase (ALT) and aspartate aminotransferase (AST) ≤ 1.5X ULN;
- Able to swallow capsules;
- Willing and able to comply with scheduled visits, treatment plan, laboratory tests, and other study procedures;

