## 8. SELECTION AND WITHDRAWAL OF PATIENTS

#### 8.1. Patient Inclusion Criteria

Diagnosis and main criteria for inclusion:

- Male and female patients 18 ≤ age ≤ 60 upon study consent;
- Screening eGFR (average of Screen A and Screen B eGFR values) ≥ 30 and ≤ 90 mL/min/1.73 m². The two eGFR values collected at Screen A and Screen B visits used to determine eligibility must have a percent difference ≤ 25%;
- Albumin to creatinine ratio (ACR) ≤ 2500 mg/g at Screen B visit;
- 4. If receiving an angiotensin converting enzyme (ACE) inhibitor and/or an angiotensin II receptor blocker (ARB), patients should be prescribed the maximally tolerated labeled daily dose (MTLDD), as defined in Section 9.1.7, for at least 6 weeks prior to the Screen A visit. The dosage of ACE inhibitor and/or ARB should remain the same throughout the remainder of the study (i.e., no change in dosage or medication), and any potential changes should be discussed with the medical monitor. Patients not taking an ACE inhibitor and/or ARB because of a medical contraindication may be eligible if they have discontinued treatment at least 8 weeks prior to the Screen A visit (these patients must be discussed with the medical monitor prior to enrollment);
- For patients enrolling in T1D Cohort:
  - Diagnosis of type 1 diabetes confirmed by fasting C-peptide level. Diagnosis must have been made ≤ 35 years of age;
  - Prescribed stable dose of insulin to maintain adequate glucose control for at least 6 months prior to the Screen A visit;
- For patients enrolling in IgAN Cohort:
  - Biopsy-confirmed IgA nephropathy;
- For patients enrolling in FSGS Cohort:
  - Biopsy-confirmed FSGS that is not due to known secondary causes including morbid obesity, decreased renal mass, viral infections, drug-induced nephrotoxicity, or prior history of vasculitis;
- For patients enrolling in ADPKD Cohort:
  - Genetic confirmation of PKD1 mutation;
- Adequate bone marrow reserve and organ function at the Screen A visit as follows:
  - Hematologic: Absolute neutrophil count > 1.5 x 10^3/L, platelets > 100 x 10^3/L, hemoglobin (Hgb) ≥ 9 g/dL;
  - b. Hepatic: Total bilirubin (TBL) ≤ 1.5X the upper limit of normal (ULN), alanine aminotransferase (ALT) and aspartate aminotransferase (AST) ≤ 1.5X ULN;
- Able to swallow capsules;

- Willing and able to comply with scheduled visits, treatment plan, laboratory tests, and other study procedures;

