7.1.3. Estimated Glomerular Filtration Rate

Estimated glomerular filtration rate (eGFR) value will be calculated at the central laboratory and used in data analyses. The equation used to calculate eGFR for each patient will be the Chronic Kidney Disease Epidemiology Collaboration (CKD-EPI) equation:

- $eGFR \text{ (mL/min/1.73 m}^2\text{)} = 141 \times \min(S_{cr}/\kappa, 1)^\alpha \times \max(S_{cr}/\kappa, 1)^{-1.209} \times 0.993^{\text{Age}} \times 1.018 \text{ [if female]} \times 1.159 \text{ [if black]}.$

Where S_{cr} is serum creatinine (mg/dL), κ is 0.7 for females or 0.9 for males, and α is -0.329 for females or -0.411 for males. Min indicates the minimum of S_{cr}/κ or 1, and max indicates the maximum of S_{cr}/κ or 1.

Historical serum creatinine and eGFR values will be treated separately from data collected as part of the trial's central lab assessments. Historical eGFR values will be calculated from historical serum creatinine results.

Missing eGFR values will not be imputed for the primary analysis of efficacy. The eGFR values collected after the window of the date of last dose for patients who do not complete study treatment will not be included in the analysis.

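### The historical eGFR analysis puts creatinine from ages 13-17 through the single CKD-EPI equation with no age rule, which can mimic pre-trial decline in the youngest patients

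*SAP*

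**What the plan says.** SAP 11.2.2 states that "Up to 5 years of historical serum creatinine values will be collected for each patient". SAP Table 5 sets the historical window at "1825 to 1 days prior to Screen A". On conversion, "eGFR will be calculated according to the equations in 7.1.3 using the patient age at laboratory collection".

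SAP 7.1.3 supplies one formula: "The equation used to calculate eGFR for each patient will be the Chronic Kidney Disease Epidemiology Collaboration (CKD-EPI) equation". Its inputs are serum creatinine, age, sex and race. The same section says that "Historical eGFR values will be calculated from historical serum creatinine results", so an eGFR reported by the local laboratory is not used, and this rule alone decides how a minor's record is treated.

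The lower age limit is 18 wherever it appears. Protocol 8.1 has "Male and female patients 18 ≤ age ≤ 60 upon study consent"; the protocol synopsis has "Male and female patients 18 ≤ age ≤ 65 upon study consent". The upper limits disagree, but the lower one does not.

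The historical values are then used in full: "all eGFR values will be used in the statistical model described in Section 11.2.3". SAP 11.2.3 compares the historical eGFR course with the course on bardoxolone methyl, by cohort, with confidence intervals and p-values. The visible text of 11.2.2 and 11.2.3 sets no minimum age at collection, no other equation for minors, and no exclusion of values from before 18.

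**The concern.** A five-year look-back from an entry age of 18 reaches adolescence. An equation without a growth term reads any rise in creatinine as a fall in GFR. If part of that rise came from growth while true GFR was unchanged, the early values compute too high and the later ones fall towards the baseline. The result looks like natural decline before the trial.

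That is the quantity against which the on-treatment change is set. The trial is open-label with no reference therapy, so in the visible plan the patient's own history serves as the comparator for slope. A historical slope that is too steep makes the change on drug look better. SAP 3 allows planned analyses to go into regulatory submissions and manuscripts, so a one-directional artefact is worth removing even if it is small.

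**Working it through.** The documents give no historical slope, no bias estimate and no count of patients aged 18-22, so there is no plan figure to reproduce. The check has four steps.

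**1. How far back the window reaches.** Earliest age = age at consent − 1825/365.25, that is, about 5.0 years earlier (consent is taken at Screen A, where the window ends).

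| Exact age at consent | Earliest age in window | Share of window before 18 |
|---|---|---|
| 18 | 13.0 | about 100% |
| 19 | 14.0 | about 80% |
| 20 | 15.0 | about 60% |
| 21 | 16.0 | about 40% |
| 22 | 17.0 | about 20% |
| 23 | 18.0 | 0% |

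**2. What the equation does.** The age term gives 0.993^(−5) = 1.036 over five years, or 60 × 0.036 = 2.1 units at an eGFR of 60. This applies to any five-year span at any age, so it is not specific to minors. A larger error needs creatinine to have been lower at 13 for the same true GFR. With creatinine above κ, the factor for creatinine lower by a fraction q is (1 − q)^(−1.209). The values of q are assumptions. For a male with eGFR 60 at 18:

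| q at age 13 | Creatinine factor | eGFR computed at 13 | Apparent loss per year, age term included |
|---|---|---|---|
| 0% | 1.000 | 62.1 | 0.4 |
| 10% | 1.136 | 70.6 | 2.1 |
| 20% | 1.310 | 81.4 | 4.3 |
| 30% | 1.539 | 95.6 | 7.1 |

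**3. Average over patients aged 18-22.** Assumptions: six yearly values from five years before entry to entry, true eGFR constant at 60, log creatinine rising linearly from 13 to 18 and then flat, ages spread evenly from 18 up to 23. The common age term is left out, so only the growth part counts. The slope is least squares: Σ(t − t̄)y / 17.5.

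Example: consent at exactly 18 with q = 30% gives yearly values of 92.3, 84.7, 77.7, 71.3, 65.4 and 60.0, a slope of −6.5 per year. At 20 the slope is −3.7, at 22 it is −0.8, and at 23 it is 0. Averaged over the age band, the spurious slope is 0, −0.8, −1.8 and −3.0 per year for q = 0%, 10%, 20% and 30%.

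**4. Dilution into the cohort.** With uniform ages (assumed), the share aged 18-22 is 5/43 = 11.6% for 18-60 and 5/48 = 10.4% for 18-65. In a cohort of 25 that is 2.9 or 2.6 patients. About half of their window lies before 18 on average, so 5%-6% of historical values are affected. Cohort mean bias = share × average from step 3, for example 0.116 × 3.0 = 0.35.

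| q | Ages 18-60 | Ages 18-65 |
|---|---|---|
| 0% | 0 | 0 |
| 10% | −0.09 | −0.08 |
| 20% | −0.21 | −0.18 |
| 30% | −0.35 | −0.31 |

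Units are mL/min/1.73 m2 per year.

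**The case against.** The strongest objection is that the size rests on assumptions. The documents do not say that CKD-EPI is limited to adults, that it is biased below 18, or that creatinine rises through adolescence at constant GFR. They give no age distribution, and no patient is shown to have records from before 18. This stands. It is why the range starts at zero, and why the point is that the rule can bias the comparison.

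A reader might go further and infer that the plan does overstate past eGFR and creates a decline. The documents do not support that. A true decline at those ages is also possible, and the age term alone is common to patients of every age.

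A reader might also infer that one young patient with many records could dominate a cohort. That cannot be shown. The model code in SAP 11.2.3 is redacted, so how rows are weighted or grouped by patient is not visible. In the yearly summaries, values are averaged within patient first.

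Two further points limit the reach. SAP 11.2.2 keeps historical data apart from central-laboratory data, and SAP 11.2.3 lists all of it, so affected records would be visible. The cohort bias is also small beside the eGFR increases of 6.4 to 9.0 mL/min/1.73 m2 in the protocol's Table 3 for the CKD studies, although those are changes and not yearly slopes.

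What remains is a stated rule that sends minors' creatinine through one equation without a condition or a justification. SAP Table 8 does separate AST limits at age 18, but it supplies no rule for eGFR.

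**Conclusion.** The point holds as a minor one. The documents establish the route: entry at 18, a five-year look-back, and one equation without a growth term applied at the age of collection. For patients aged 18-22 at consent, between about 100% and about 20% of the window falls at ages 13-17.

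The size is conditional. With creatinine 0%-30% lower at 13 than at 18 for the same GFR and an eGFR of 60, the spurious historical decline is 0 to 3.0 mL/min/1.73 m2 per year on average in these patients, and 0 to 0.35 per year in the cohort mean slope if ages are uniform. If no such patient enrols with early records, or if creatinine did not change with growth, the effect is nil. Any effect would favour the drug. Because the model code is hidden, its exact effect on the reported contrast cannot be computed.

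Only the additional historical-slope analysis and its yearly summaries are exposed. It would be wrong to read this as a doubt about the primary result: the Week 12 MMRM in SAP 11.1 uses on-study central-laboratory values from patients aged 18 or older.

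**What to change.** Add to SAP 11.2.2: historical creatinine enters the statistical model and the yearly summaries only if collected at age 18 or older; earlier values are listed but neither modelled nor summarised; the number of patients and records excluded is reported by cohort. The same filter should apply to the requirement in 11.2.3 of at least one historical value, so that a patient whose whole history predates 18 leaves that analysis.

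The cost is a sentence or two in the SAP and one filter in the dataset program. The downside is the loss of a few historical records for the youngest patients, and possibly of a patient who consents at 18. Keeping these values with a written justification of the equation at those ages would also close the gap, but the filter removes this source of bias without needing one.

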5.3.1. Efficacy Measurement and Variable

Central laboratory reported eGFR values will be used to calculate change from baseline in eGFR, the primary efficacy endpoint for the study. Baseline eGFR value will be calculated as described in Section 7.2.1 below.

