11.2.3. Statistical Model

The general linear model will be run according to the year labels in Table 5.

The table summaries will report the historical change in eGFR vs. baseline (with no post-baseline eGFR values from PHOENIX in the model), and the change in eGFR vs. baseline on bardoxolone methyl treatment for patients who have historical serum creatinine values reported.

Only patients at least one historical eGFR value entered will be included in the analysis.

The change in eGFR will be analyzed by an analysis of covariance, with baseline eGFR and natural log(Baseline ACR) as covariates:

[REDACTED]

[REDACTED]

The LSMeanDiffCL will compare historical eGFR slopes and eGFR slope in PHOENIX along with appropriate confidence intervals, and the Diff results will provide the appropriate p-values. Results will be summarized by cohort.

Summary statistics of the datasets listed in [Table 5](#) by analysis time point will also be summarized.

All historical eGFR data will be listed.

[REDACTED]

[REDACTED]

[REDACTED]

[REDACTED]

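### In the additional historical comparison, local-laboratory eGFR is anchored to a central-laboratory baseline, so a mean local-central offset biases the before-versus-on-drug contrast

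*SAP*

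**What the plan says.** **Source of the historical values.** SAP 11.2.2 collects up to five years of past serum creatinine and states: "Historical serum creatinine values will have been analyzed at various local laboratories (i.e., not collected as part of central lab data"). SAP 7.1.3 adds: "Historical eGFR values will be calculated from historical serum creatinine results".

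**Source of the trial values.** SAP 5.3.1: "Central laboratory reported eGFR values will be used to calculate change from baseline in eGFR". Protocol 9.10.20 lists the trial creatinine as enzymatic. Neither document states a method for the local laboratories.

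**Baseline in the historical dataset.** SAP 11.2.2: "The eGFR values used in the analysis datasets for the baseline label will be the baseline eGFR values for each patient (defined in 7.2.1"). SAP 7.2.1 averages the Day 1 and Screening eGFR values from the trial, so this anchor is central. It is placed at year zero.

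**Handling of the two sources.** SAP 7.1.3 says: "Historical serum creatinine and eGFR values will be treated separately from data collected as part of the trial's central lab assessments". SAP 11.2.2 repeats this, but its next paragraph says: "One dataset will be generated with the baseline eGFR values, baseline log(ACR) values, the historical eGFR values, and the eGFR results in PHOENIX".

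**The comparison.** SAP 11.2.3: "The table summaries will report the historical change in eGFR vs. baseline", with no on-treatment values in that model, and beside it the on-treatment change against the same baseline. The two are then compared with confidence intervals and p-values. The readable covariates are baseline eGFR and log baseline ACR. On who enters: "Only patients at least one historical eGFR value entered will be included in the analysis".

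**The concern.** The two sides of the contrast are not measured alike. Historical change runs from a local value to a central value, whereas on-treatment change runs from central to central. A systematic difference between the laboratories looks like a change in kidney function before the trial and cancels on the treatment side. If local laboratories on average read creatinine lower than the central one, historical eGFR is too high, prior decline is exaggerated and the apparent benefit grows. If they read higher, prior decline is hidden and the benefit shrinks. A larger sample does not remove a mean offset.

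The trial has no control arm, so readers will look to each patient's own history for context. A patient with a single historical value is the most exposed, because that patient's historical change is entirely a cross-laboratory difference.

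**Working it through.** The documents give no figure for this comparison, so there is none to reproduce. The stated 80% power with 25 patients belongs to the primary test.

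**Step 1. How an offset enters.** Let central eGFR equal the true value and local eGFR equal the true value plus *b*.
- Historical minus baseline: (true history + *b*) − true baseline, shifted by *b*.
- On treatment minus baseline: shifted by 0.
- Contrast between them: shifted by the whole of *b*.

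**Step 2. Size on the change-versus-baseline reading.** Formula (CKD-EPI, SAP 7.1.3; male, not black, creatinine above 0.9 mg/dL): eGFR = 141 × (SCr/0.9)^−1.209 × 0.993^age. Age 45 is assumed. Local creatinine is taken as higher than central by an assumed amount, since the documents give no offset.

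| Central SCr (mg/dL) | eGFR | Shift at 0.05 mg/dL | Shift at 0.10 mg/dL |
|---|---|---|---|
| 2.1 | 36.9 | 1.0 | 2.0 |
| 1.5 | 55.4 | 2.2 | 4.2 |
| 1.1 | 80.6 | 4.2 | 8.1 |

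A local reading lower by the same amounts gives slightly larger shifts of opposite sign: 1.1/2.2, 2.3/4.8 and 4.7/9.9. All three eGFR levels lie inside the eligibility range of 30 to 90.

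For scale, protocol 5.1.1 reports mean gains of 5.5 (Phase 3 trial, eGFR 15 to 29) and 7.4 (Phase 2b trial, baseline 32.4). At eGFR 37, the level nearest those trials, 0.05 mg/dL is 1.0/7.4 to 1.0/5.5, or about 14 to 18% of the gain.

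**Step 3. Size on the slope reading.** Take a flat true course, put *b* = 1 on every historical value and 0 on the central baseline at year zero, and fit a least-squares line.

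| Historical values (years) | Slope shift per unit of offset, baseline included | Baseline excluded |
|---|---|---|
| −5, −4, −3, −2, −1 | −0.14 per year | 0 |
| −2.5, −2, −1.5, −1 | −0.38 per year | 0 |
| −1 only | −1.0 per year | not estimable |
| −0.5 only | −2.0 per year | not estimable |

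To put these on the scale of the on-treatment slope, assume a gain of 5.5 reached linearly by Week 12. Then 84/365.25 = 0.23 year, and 5.5/0.23 is about 24 per year. An offset of 2.2 (0.05 mg/dL at eGFR 55) shifts the historical slope by:
- 2.2 × 0.14 = 0.3 per year with yearly values over five years, about 1% of 24;
- 2.2 × 1.0 = 2.2 per year with one value at −1 year, about 9%;
- 2.2 × 2.0 = 4.4 per year with one value at −0.5 year, about 18%.

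**Step 4. What removes it.** The last column shows that a constant offset drops out of a slope fitted to local values alone.

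**The case against.** **The SAP says the sources are treated separately.** It does, and this shows that the difference was noticed. But both sources go into one dataset with a central baseline, and the readable text describes no calibration, laboratory term or sensitivity analysis for it. The model code is redacted, so a laboratory term cannot be excluded. The sponsor can settle this by stating it in the text.

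**The quantity may be a slope.** SAP 11.2.3 uses both words, change against baseline and slope, and SAP 11.2.2 builds a continuous year variable. This objection stands as to size: one-for-one carry-over holds only for the change reading. On the slope reading bias remains, because the central baseline sits at year zero, but it is a much smaller share of the on-treatment slope.

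**The offset is assumed.** True. With several local laboratories, offsets of opposite sign partly cancel and add variance. Only their mean is bias.

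A reader might infer four stronger things that the documents do not support:
- *The drug effect is overstated.* The direction is unknown.
- *A third or more of the effect could be artefact.* That depends on the assumed offset, the eGFR level and the reading. Setting the shift at eGFR 81 against gains seen at eGFR near 30 mixes populations. In the study listed with baseline eGFR 82 (pulmonary hypertension), the placebo-corrected gain was 14.7.
- *History is the only internal comparison.* SAP 12.7.1 analyses eGFR at Week 16 after withdrawal, although that does not estimate prior decline. Much of SAP 11.2 is also redacted.
- *The primary result is affected.* It compares central values with central values.

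**Conclusion.** The point holds for the additional historical comparison in SAP 11.2.2 and 11.2.3. As written, local history is measured from a central baseline, and a tested contrast carries any mean local-central offset. On the change reading the offset enters in full: 1.0, 2.2 or 4.2 mL/min/1.73 m² at eGFR 37, 55 or 81 for an assumed 0.05 mg/dL. On the slope reading it is about 0.14 to 1.0 per year per unit of offset for the spread of records considered, and more if a lone value lies closer to baseline.

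This rests on an assumed offset common to all patients, age 45, male, and a redacted model with no laboratory term beyond the stated covariates. The primary Week 12 analysis is not touched. The change is worth making because it is cheap and removes a constant offset from an analysis that will report p-values. It does not call the trial's main conclusion into question.

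**What to change.** Amend SAP 11.2.2 and 11.2.3 as follows.

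1. Estimate the historical annual rate from local values only, in patients with at least two historical values, without the central baseline as an end point.
2. Estimate on-treatment change from central values only.
3. State a common time scale before contrasting them. For example, compare the observed Week 12 change with the change expected over 12 weeks at the historical rate (annual rate × 0.23).
4. Report how many patients have a single historical value, and show the currently planned all-patient analysis alongside, so that any selection from leaving them out is visible.
5. Use a local/central indicator only in a slope model with at least two historical values per patient. In a model built on the Table 5 time-point labels it is aliased with the Historical label and cannot be estimated.
6. State the limit: a local-only slope removes a constant offset, but not a change of laboratory within one patient's history.

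The cost is SAP text and programming, with no new data. The downside is fewer patients, in cohorts of about 25, and a less precise historical rate.
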